3. PARTICIPANT SELECTION

3.1 Eligibility Criteria

Participants must meet the following criteria on screening examination to be eligible to participate in the study:

- 3.1.1 Patients must have a biopsy proven unresectable or locally recurrent intrahepatic cholangiocarcinoma. Otherwise, patients must have a diagnosis of an unresectable or locally recurrent hepatocellular cancer using either pathology of the liver tumor or radiologic imaging and an elevated AFP. Patients with a single lesion must be 12 cm or less in greatest dimension. For patients with two lesions, no lesion may be greater than 10 cm in greatest dimension. For patients with three lesions, no lesion may be greater than 6cm in greatest dimension. Patients may have

single or multinodular tumors (up to 3). There must be no evidence of extrahepatic tumor. Portal vein involvement or thrombosis is allowed.

- 3.1.2** Participants must have measurable disease, defined as at least one lesion that can be accurately measured in at least one dimension (longest diameter to be recorded) as ≥ 20 mm with conventional techniques or as ≥ 10 mm with spiral CT scan. See Section 10 for the evaluation of measurable disease.
- 3.1.3** Patients may have had prior chemotherapy, targeted biological therapy (ie sorafenib, etc...), surgery, transarterial chemoembolization (TACE), radiofrequency ablation, or cryosurgery for their disease. 5-fluorouracil, capecitabine and sorafenib must be discontinued prior to study entry, with no wash-out period required. Nitrosoureas and mitomycin C must be discontinued at least 6 weeks prior to study entry. All other agents must be discontinued at least 4 weeks prior to study entry. Patients may not have had prior radiation to the affected area.
- 3.1.4** Patients must be 18 years of age or older.
- 3.1.5** Expected survival must be greater than three months.
- 3.1.6** ECOG performance status ≤ 2 .
- 3.1.7** Participants must have normal organ and marrow function as defined below, all of which must be obtained within two weeks prior to study registration date:
- Absolute neutrophil count $\geq 750/\text{mcL}$
 - Platelets $\geq 25,000/\text{mcL}$
 - Total bilirubin $\leq 4.0 \times$ institutional upper limit of normal
 - AST (SGOT)/ALT (SGPT) $\leq 6.0 \times$ institutional upper limit of normal

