8. CORRELATIVE/SPECIAL STUDIES

8.1 Circulating Biomarkers

Participation in the correlative blood sample studies will be offered to study participants at MGH only.

Based on findings from preliminary studies, we propose here to evaluate the changes in blood circulating SDF1 α and circulating myeloid cells before, during, and after a three-week schedule of proton beam radiation therapy, and to explore potential associations between the changes in these biomarkers and resistance to treatment. In exploratory studies, we will evaluate several other cytokines using multiplex protein array (Meso-Scale Discovery, Inc.).

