8.1.1 Experimental Design

CONFIDENTIAL

This document is confidential. Do not disclose or use except as authorized.

Blood will be drawn by venipuncture, and the first 7-10 ml blood will be excluded or used for other analysis. The following 8 ml will be collected in an EDTA tube. The EDTA tube with the blood sample will be shipped in wet ice within 2 hours of drawing for further processing at Steele Laboratory at MGH. We will analyze the correlation between plasma SDF1 α and circulating myeloid cells with multiple measures of outcome (ORR, TTP, OS) in advanced liver cancer patients after proton beam radiation therapy.

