8.2 Genotype Testing

Next generation sequencing and tissue-based testing on specimens of patients at MGH will assess exploratory tissue markers in relation to worsening local control and will potentially inform future trials.

Next generation sequencing assays have been developed by the Massachusetts General Hospital Center for Integrated Diagnostics (MGH CID) to detect a wide variety of alterations in cancer genes that could alter response to therapy. The 1K Cancer Panel provides for the evaluation of small nucleotide variants (SNVs) and insertion/deletions (indels) across ~800 cancer genes using tumor DNA. The Solid Tumor Fusion Panel can detect gene fusions across ~50 gene targets using complimentary DNA (cDNA). Both of these approaches generate target-enriched libraries that undergo next-generation sequencing on an Illumina platform. A blood sample is used as a control to identify alterations that occur specifically in the tumor tissue. All testing and sequence analysis will be performed in the MGH Translational Research Laboratory (MGH TRL) within the MGH CID.

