8.2.1 Sample Shipment

- a) Formalin-fixed, paraffin-embedded (FFPE) intrahepatic cholangiocarcinoma and hepatocellular carcinoma tissue samples will be submitted for genotype testing as either the FFPE block or as 15 sections of tissue (5 microns) that have been cut from the block and mounted onto plus microscope slides.
- b) Slides must be sent secured in appropriate slide holders and FFPE blocks in a crush-proof container to the following address by overnight courier, under ambient conditions:

Massachusetts General Hospital

[REDACTED]

- c) A whole blood sample collected on protocol will also be sent to the same address above, on cold packs by overnight carrier. Appropriate IATA shipping of dangerous goods regulations must be followed. Patients at external sites will have a one-time blood sample drawn and sent to the same address above.
- d) Quality assurance measures require that each patient sample is submitted with the protocol number and two unique identifiers (i.e. surgical number, patient ID number, patient initials). An email must also be sent to the MGH TRL centralized mailbox [REDACTED] indicating intent to submit the sample, the trial number, and the relevant sample identifiers. The MGH TRL program coordinator will verify receipt of the sample, whether the sample was received in acceptable condition and specified amount, and will confirm the identifiers before initiating the testing process.

CONFIDENTIAL

This document is confidential. Do not disclose or use except as authorized.

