14.2 Sample Size/Accrual Rate

The accrual goal was previously revised to 60 patients in order to preserve high power for detecting a slightly smaller but clinically significant increase in local control to 80% at 2 years. Recently, emerging data suggest unresectable liver tumors represent clinically heterogeneous groups, in particular, intrahepatic cholangiocarcinomas are associated with a more favorable prognosis than primary hepatocellular cancers. Thus we propose to restrict the primary hypothesis in 14.1 to the major tumor group, namely patients with unresectable primary hepatocellular cancer. As intrahepatic cholangiocarcinomas constitute one-third of the present enrollment, we propose to continue with their accrual in order to estimate their failure and survival endpoints with reasonable precision for planning future studies for the specific population. Based on the observed distribution of the tumor groups, the target accrual is increased to a total of 90 patients in order to obtain 60 patients with unresectable primary hepatocellular cancer for testing the primary hypothesis in 14.1.

CONFIDENTIAL

This document is confidential. Do not disclose or use except as authorized.

Since the protocol was activated by MD Anderson Cancer Center at the end of September 2010, 47 patients have been enrolled by two participating institutions over a period of 13 months. As of March 2013, their combined accrual has reached 57 patients. We project the increased sample size will be reached within the next year and a half, as the protocol has expanded recently to a third institution. **If a patient is found to be ineligible once registered and therefore taken off study and excluded from analysis, an additional patient may be enrolled and included in analysis.** As specified in 5.6, the patients will be followed for at least 5 years from the completion of protocol treatment or until death, whichever occurs first.

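### The exploratory marker analyses in 8.1.1 and 8.2 carry no histology term, so a marker that only tracks tumour type may appear associated with outcome

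*Combined protocol and SAP*

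**What the plan says.** **Circulating markers.** Section 8.1 states the aim as "to explore potential associations between the changes in these biomarkers and resistance to treatment". Section 8.1.1 gives the analysis: a correlation of plasma SDF1 alpha and circulating myeloid cells "with multiple measures of outcome (ORR, TTP, OS) in advanced liver cancer patients after proton beam radiation therapy". On who takes part: "Participation in the correlative blood sample studies will be offered to study participants at MGH only". The number of such patients is not given.

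**Genotype.** Section 8.2 says that testing "will assess exploratory tissue markers in relation to worsening local control". Section 8.2.1 shows that both tumour types enter: "intrahepatic cholangiocarcinoma and hepatocellular carcinoma tissue samples will be submitted for genotype testing".

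**Histology elsewhere in the plan.** Section 14.2 says that "intrahepatic cholangiocarcinomas are associated with a more favorable prognosis than primary hepatocellular cancers" and for that reason restricts the primary hypothesis to HCC. Section 2.3 cites emerging HCC data that differ from the combined historical data in both survival and local control. Section 14.4 expects failure and survival to be estimated separately by tumour type, and 1.3.4 makes cholangiocarcinoma a descriptive objective of its own.

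**Section 14 on markers.** It has no analysis plan for the correlative studies. Section 14.4 covers toxicity, response, failure patterns and survival, and 14.3 lists stratification factors as not applicable.

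**The concern.** The correlative question is whether a marker goes with resistance to proton treatment. By the plan's own account, tumour type is related to outcome. If a marker also differs by tumour type, an analysis that ignores tumour type mixes two things: any relation within HCC or within cholangiocarcinoma, and the difference between the two diseases. The second can produce an association when the first is absent.

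This can arise for a baseline level, for a genotype, and for a change on treatment if the change itself differs by tumour type. At stake is the interpretation of the exploratory results. Section 8.2 hopes that they will inform future trials, and 14.2 foresees future studies specific to cholangiocarcinoma.

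**Working it through.** **1. The plan's own figures.** The only stated operating characteristics belong to the primary HCC test: 30 evaluable patients, success if at least 21 are locally controlled, 55% against 80%.
- Power: P(X ≥ 21 | n = 30, p = 0.80) = 0.939, against the stated 94%.
- Type I error: P(X ≥ 21 | n = 30, p = 0.55) = 0.069, against the stated 7%.
- Accrual: 60 / (1 − 1/3) = 90, as in 14.2.

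All three reproduce, and the present point does not touch them. There is no stated sample size, alpha or power for the marker analyses.

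**2. Inputs for sizing the effect on overall survival.**
- From the documents: one-third cholangiocarcinoma (14.2); HCC 2-year overall survival 50% (14.1).
- Assumed: 45 or 60 MGH patients with the same 2:1 mix; death hazard ratio, cholangiocarcinoma to HCC, 0.7 or 0.5; marker mean differing by 0.5 or 1.0 SD between tumour types; no marker effect within either type; exponential survival; censoring uniform over 36 to 60 months.
- Meaning of the hazard ratios: 0.5^0.7 = 0.62 and 0.5^0.5 = 0.71, so the assumed cholangiocarcinoma 2-year survival is about 62% or 71%.

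**3. Method.** Cox score test of the marker at two-sided 5%, 8,000 simulated trials per setting, first ignoring histology and then stratified by it.

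| Patients | Hazard ratio | Marker shift | Rejected, histology ignored |
|---|---|---|---|
| 45 | 0.7 | 0.5 SD | 6.5% |
| 45 | 0.7 | 1.0 SD | 7.0% |
| 45 | 0.5 | 0.5 SD | 6.8% |
| 45 | 0.5 | 1.0 SD | 11.4% |
| 60 | 0.7 | 0.5 SD | 5.7% |
| 60 | 0.7 | 1.0 SD | 8.0% |
| 60 | 0.5 | 0.5 SD | 7.1% |
| 60 | 0.5 | 1.0 SD | 13.4% |

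The stratified test rejects in 4.6% to 5.5% of trials throughout.

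**4. Wider range.** A second simulation (3,000 trials per setting, censoring uniform over 2 to 5 years) took 30 to 90 patients, 90 being the whole trial and so an upper bound, and marker shifts of 1 to 4 SD. The hazard ratio is ln(cholangiocarcinoma 2-year survival) / ln(0.5).

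| Cholangiocarcinoma 2-year survival | Hazard ratio | Rejected, histology ignored |
|---|---|---|
| 50% | 1.00 | 5% to 6% |
| 60% | 0.74 | 6% to 16% |
| 70% | 0.51 | 8% to 48% |
| 80% | 0.32 | 13% to 86% |

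The stratified test rejects in 4.5% to 6.4% over all settings. With 45 patients and 70% survival, ignoring histology gives 10%, 18% and 27% for shifts of 1, 2 and 4 SD.

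**5. Limits.** Only overall survival was simulated. No rate was computed for response, time to progression or local control.

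**The case against.** **Pooling is not stated.** Section 8.1.1 names a population, not a model, and 8.2.1 is a shipping instruction. Since 2.3 and 14.4 treat the tumour types separately, an analyst might do the same for markers. This stands as far as it goes: a reader might infer that the plan commits to an unadjusted pooled analysis, and no sentence says so. What remains is that the text describes one mixed population, gives no histology term, and so permits pooling.

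**The inflation is modest.** A reader might infer that a marker tracking histology is bound to look like a marker of resistance. The documents do not support that. They give no hazard ratio, marker difference or MGH sample size, and under the moderate assumptions above most such markers would not be flagged.

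**Within-patient change.** Section 8.1 is about changes, and a fixed difference in level between tumour types cancels in a change. This stands for change scores. It does not cover 8.1.1, which speaks of plasma SDF1 alpha without limiting it to change, nor genotype, which has no change to take.

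**Local control.** Section 14.2 speaks of prognosis in general. Only 2.3 mentions local control, comparing HCC with combined historical data and giving neither size nor direction. This stands: support for the genotype part is thin.

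**Tissue availability.** A reader might also infer that the genotyped set is skewed towards cholangiocarcinoma, which must be biopsy proven, whereas HCC may be diagnosed "using either pathology of the liver tumor or radiologic imaging and an elevated AFP". The documents do not say how many HCC patients lack tissue or what the MGH mix is, so no size can be given. Stratifying would not recover those patients in any case.

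**Exploratory status.** The marker work is labelled exploratory, is absent from the objectives in 1.2 and 1.3, and has no decision rule. The 5% level is a yardstick adopted here. This stands and limits the weight of the point.

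**Conclusion.** The point holds as a minor one. The marker analyses in 8.1.1 and 8.2 are open to confounding by histology, in a plan that itself says the tumour types differ in prognosis. For overall survival, a marker with no effect within either type would be declared associated in about 6% to 13% of trials instead of 5%. This assumes 45 to 60 MGH patients, a hazard ratio of 0.5 to 0.7 and a marker shift of 0.5 to 1 SD. The rate rises with larger assumed gaps, and there is no excess if outcomes do not differ. Stratification brings it back to about 5%. The case is weaker for genotype against local control. The primary HCC conclusion, with its 94% power and 7% error, is unaffected.

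**What to change.** Add one sentence to 8.1.1 and one to 8.2: exploratory marker-outcome analyses will be stratified by, or adjusted for, histology (HCC or cholangiocarcinoma), and the HCC estimate will also be shown separately. Suitable forms are a stratified Cox or log-rank analysis for time to progression, overall survival and local failure, and a Mantel-Haenszel analysis for response.

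Histology is already recorded for every patient, so no new data, visits or samples are needed. The cost is a small loss of information from comparing within tumour type in what may be a small sample.

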8.1.2 Collection

To this end we will measure circulating biomarkers

- (i) pretreatment
- (ii) during proton beam radiation therapy at days 1, 8, 15 and the last day of radiation treatment
- (iii) one month post-completion of the proton beam radiation treatment; and
- (iv) at the time of disease progression

Samples will be collected at the following time points-

- a. Prior to the start of therapy
- b. Within 72 hours of start of therapy.
- c. Day 8, 15 and the day of the last radiation treatment.
- d. 1 month after completion of therapy.
- e. following radiologic progression

8.1.3 Shipping Instructions

The tube containing the blood should be shipped with the following information

1. Study Number at the DF/HCC
2. Patient number on the study
3. Patient's initials
4. Treating physician's name
5. Date of collection
6. Date of shipping

The tube of blood should be placed in a sealable container and placed in a box with the necessary information. The box should be marked Biohazard.

[REDACTED]
[REDACTED]
[REDACTED]

CONFIDENTIAL

This document is confidential. Do not disclose or use except as authorized.

[REDACTED]

8.2 Genotype Testing

Next generation sequencing and tissue-based testing on specimens of patients at MGH will assess exploratory tissue markers in relation to worsening local control and will potentially inform future trials.

Next generation sequencing assays have been developed by the Massachusetts General Hospital Center for Integrated Diagnostics (MGH CID) to detect a wide variety of alterations in cancer genes that could alter response to therapy. The 1K Cancer Panel provides for the evaluation of small nucleotide variants (SNVs) and insertion/deletions (indels) across ~800 cancer genes using tumor DNA. The Solid Tumor Fusion Panel can detect gene fusions across ~50 gene targets using complimentary DNA (cDNA). Both of these approaches generate target-enriched libraries that undergo next-generation sequencing on an Illumina platform. A blood sample is used as a control to identify alterations that occur specifically in the tumor tissue. All testing and sequence analysis will be performed in the MGH Translational Research Laboratory (MGH TRL) within the MGH CID.

8.2.1 Sample Shipment

- a) Formalin-fixed, paraffin-embedded (FFPE) intrahepatic cholangiocarcinoma and hepatocellular carcinoma tissue samples will be submitted for genotype testing as either the FFPE block or as 15 sections of tissue (5 microns) that have been cut from the block and mounted onto plus microscope slides.
- b) Slides must be sent secured in appropriate slide holders and FFPE blocks in a crush-proof container to the following address by overnight courier, under ambient conditions:

Massachusetts General Hospital

[REDACTED]

- c) A whole blood sample collected on protocol will also be sent to the same address above, on cold packs by overnight carrier. Appropriate IATA shipping of dangerous goods regulations must be followed. Patients at external sites will have a one-time blood sample drawn and sent to the same address above.
- d) Quality assurance measures require that each patient sample is submitted with the protocol number and two unique identifiers (i.e. surgical number, patient ID number, patient initials). An email must also be sent to the MGH TRL centralized mailbox [REDACTED] indicating intent to submit the sample, the trial number, and the relevant sample identifiers. The MGH TRL program coordinator will verify receipt of the sample, whether the sample was received in acceptable condition and specified amount, and will confirm the identifiers before initiating the testing process.

CONFIDENTIAL

This document is confidential. Do not disclose or use except as authorized.

9. STUDY CALENDAR

9.1 Required Data

Lab evaluations must be completed within 2 weeks of study entry. All other baseline assessments must be completed within 6 weeks of study entry. All study assessments should be administered +/- 3 days of the protocol-specified date, unless otherwise noted.

Data Set	Prior to Study Entry	Weekly Visit During Radiation Therapy	At Follow-Up (3)
Age	X		
Sex	X		
H&P (including clinical assessment of ascites and encephalopathy at baseline and follow up)	X	X	X
Toxicity Assessment	X	X	X
Vital Signs (pulse, blood pressure, temperature)		X	
CBC with diff (WBC, HGB, PLT, ANC, ALC)	X	X	
PT/INR, Albumin, Child-Pugh classification	X		X
Renal Function Tests (BUN, creatinine, calculated creatinine clearance per Cockcroft & Gault)	X	X	
Liver Function Tests (SGOT, SGPT, T bili, Alk Phos) & LDH	X	X	X
Tumor markers (CEA, CA 19-9) Alpha Fetal Protein	X	X	X
Beta-HCG (women of child-bearing potential)	X		
Tumor Measurement	X		twice yearly (1)
Abdominal and Pelvic CT and/or hepatic MRI	X		twice yearly (1)
Thoracic CT	X		twice yearly
Peripheral Blood for correlative studies (optional)	X	X (2)	X (2)

Notes:

(1) Imaging and tumor measurements in follow up are required for study data twice yearly. Additional imaging studies may be obtained for clinical follow up at the discretion of the treating clinicians. For study participants who receive follow up care at institutions other than the treating institution, imaging reports and scans must be sent to the treating institution to be included in the study data set.

(2) Peripheral blood will be obtained with clinical labs at pretreatment, during proton beam radiation therapy at days 1, 8, 15 and the last day of radiation treatment. (this blood draw is optional and will be offered to study participants at MGH only)

CONFIDENTIAL

This document is confidential. Do not disclose or use except as authorized.

(3) Follow up assessments will be due at 1, 3, 6, 9, 12, 15, 18, 21, 24, 30, 36, 42, 48, 54, and 60 months post treatment, with a visit window of +/- 3 weeks for the 1 month follow up and +/- 6 weeks for all other follow up dates.

9.2 Data Collection

Weekly on-study labs are to be drawn on study days 1, 8, 15 and the day of the last radiation treatment. All patients will be evaluated initially, and at 1, 3, 6, 9, 12, 15, 18, 21, 24, 30, 36, 42, 48, 54, and 60 months post treatment. Each follow-up examination will consist of interval history and physical examination, toxicity assessment, liver function tests, LDH, PT INR, albumin, Child-Pugh classification and tumor markers (CEA, CA 19-9, alpha feta protein). Baseline and follow up physical examination will include clinical assessment of encephalopathy and ascites for calculation of Child-Pugh Score. Assessment of the liver tumor by CT and/ or MRI will be performed at time of abdominal imaging twice yearly for two years and then yearly for three years. Chest CT will be obtained twice yearly for two years and then yearly for three years. Additional imaging studies may be obtained for clinical follow up at the discretion of the treating clinicians. For study participants who receive follow up care at institutions other than the treating institution, imaging reports and scans must be sent to the treating institution to be included in the study data set.

10. MEASUREMENT OF EFFECT

10.1 Toxicity and Complications

Acute and late morbidity of radiation treatment will be scored using the Common Terminology Criteria for Adverse Events 3.0 (CTCAE 3.0; see Appendix 11)

10.2 Tumor Response: RECIST Criteria

Complete Response (CR): Disappearance of entire lesion, with no additional evidence of disease
Partial Response (PR): At least a 30% decrease in the sum of the longest diameter (LD) of the primary lesion, taken as reference the baseline sum LD.

Progressive Disease (PD): At least a 20% increase in the LD of the lesion, taken as the reference the smallest sum LD recorded since the treatment started or the appearance of one or more new lesions

Stable Disease (SD): Neither sufficient shrinkage to qualify for PR nor sufficient increase to qualify for PD, taking as reference the smallest sum LD since the treatment started.

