- While radiation can cause mucosal ulceration, other tissues may be damaged which may require surgery and may be life-threatening.

- Stomach and bowel are protected well from excessive dose of radiation. However, overdosing the stomach or bowel can lead to ulceration or perforation.
- Pain, inflammation or scarring of your kidneys, stomach and bowel. These organs are protected well from excessive dose of radiation. Therefore, it is unlikely that patients will experience symptoms of injury to these organs
- Nerve damage
- Development of a new cancer resulting from treatment may happen many years after completing treatment
- Spinal cord injury

MRIs use powerful magnets to make images. Therefore, persons with metal implants, such as surgical clips or pacemakers should not have an MRI. However, there are no known health risks associated with this exposure. People who feel uncomfortable in confined spaces (claustrophobia) may feel uncomfortable in the narrow cylinder. The MRI makes loud banging noises as it takes images. Earplugs can be used to reduce the noises. The MRI can be stopped at any time at the request of the patient.

CT Scans: The radiation associated with these diagnostic radioactive drug and diagnostic x-ray studies will not adversely affect the treatment of the patient's disease.

Reproductive risks: Because the treatment in this study can affect an unborn baby, female patients should not become pregnant while on this study. Female patients should also not nurse a baby while on this study.

Potential benefits

The potential benefits of this treatment include shrinkage of the tumor, greater control of tumor growth, and possibly longer life.

SCHEMA

- 1. **REGISTER.**
- 2. **TREATMENT:** Proton Beam Irradiation in 15 fractions. Acute toxicity evaluation weekly during study treatment, and at 3 month follow up.
- 3. **FOLLOW-UP:** Evaluation for Tumor Response using RECIST Criteria. Evaluation for acute and late toxicity per CTCAE v. 3.0

Eligibility Criteria:

1. Patients must have a biopsy proven unresectable or locally recurrent cholangiocarcinoma, or a diagnosis of an unresectable or locally recurrent hepatocellular cancer using either pathology of the liver tumor or radiologic imaging and an elevated AFP. For patients with a single tumor, lesion may be up to 12 cm in

size. For patients with two lesions, no lesion may be greater than 10 cm in size. For patients with three lesions, no lesion may be greater than 6cm in size.

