14.4 Analysis of Secondary Endpoints

The secondary endpoints of acute and late toxicity, tumor response, failure patterns and overall survival are defined in the modality review of 10.1-10.7. Toxicity and response data will be summarized in tables, with the exact binomial confidence interval reported for their rates. Time to failure and survival will be analyzed using standard methods for failure time data, primarily the Kaplan-Meier estimate, while differences between patient subgroups may be explored using the log-rank test. In particular, the increase in sample size will provide high precision for estimating the failure and survival endpoints separately for patients with hepatocellular cancer and cholangiocarcinoma.

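### The progression rule in 10.2 sets one lesion's diameter against a sum of diameters, and for any number of lesions no rule says which category prevails when a scan meets both partial response and progression.

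*Combined protocol and SAP*

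**What the plan says.** Section 10.2 gives the response categories:

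- For partial response (PR) the text asks for "At least a 30% decrease in the sum of the longest diameter (LD) of the primary lesion, taken as reference the baseline sum LD".
- On growth, the threshold for progressive disease (PD) reads "At least a 20% increase in the LD of the lesion, taken as the reference the smallest sum LD recorded since the treatment started". A new lesion also counts as PD.
- Stable disease (SD) is the remainder: "Neither sufficient shrinkage to qualify for PR nor sufficient increase to qualify for PD", again with the smallest sum as reference.
- Complete response requires that there be no other evidence of disease. The PR definition has no such condition.

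Eligibility criterion 3.1.1 allows one, two or three lesions. Criterion 3.1.2 directs the reader onward for measurement rules: "See Section 10 for the evaluation of measurable disease". Section 10 does not say which lesion the PD sentence means, how lesions are combined for PD, which category prevails, or how a patient's overall response is derived from serial scans. The Schema names the criteria without a version: "Evaluation for Tumor Response using RECIST Criteria".

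Tumour response is a secondary objective for hepatocellular cancer (1.3.2) and for cholangiocarcinoma (1.3.4). Section 14.4 plans the analysis: "Toxicity and response data will be summarized in tables, with the exact binomial confidence interval reported for their rates". Section 8.1.1 also uses response rate and time to progression as outcomes in the biomarker work.

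**The concern.** There are two separate faults.

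The first is in the PD sentence and concerns only patients with two or three lesions. The measured quantity is one lesion's diameter and the reference is a sum over lesions. Applied as written, the rule is far too hard to meet, and clear growth falls into stable disease or stays in partial response.

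The second concerns every patient. PR is measured from baseline, while PD is measured from the smallest value or triggered by a new lesion. The two can therefore be true of the same scan, and nothing says which one counts.

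An exact binomial interval takes the numerator as settled. Here the numerator depends on choices the plan does not make. The same calls feed the time-to-progression analysis in 8.1.1.

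**Working it through.** The plan states no expected response rate or precision for 10.2, so there is no figure of that kind to reproduce. Its only design calculation concerns the primary endpoint (14.1: at least 21 of 30 free of local failure). Exact binomial tails give 0.9389 at a true rate of 0.80 and 0.0694 at 0.55, matching the stated 94% and 7%. Response is not an input to either.

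**Inputs from 10.2.** Write S0 for the baseline sum of longest diameters, Smin for the smallest earlier sum (baseline included), S for the current sum and L for the current diameter of any one lesion.

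- PR: S ≤ 0.7 × S0.
- PD, literal reading: L ≥ 1.2 × Smin.
- PD, sum reading: S ≥ 1.2 × Smin.

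**Step 1: how far the literal PD rule is off.** For k lesions of equal diameter d at the smallest sum, Smin = k × d. Literal PD needs L ≥ 1.2 × k × d, so one lesion must grow by a factor of 1.2 × k:

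- one lesion: 1.2 (the two readings agree);
- two lesions: 2.4;
- three lesions: 3.6.

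**Step 2: worked cases (mm).** All diameters are illustrative.

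| Course | Change in S from baseline | Change in S from Smin | Literal PD threshold, and largest L | PR | PD literal | PD on sum |
|---|---|---|---|---|---|---|
| 30+30 → 60+60 | 120/60 − 1 = +100% | +100% | 1.2 × 60 = 72; L = 60 | no | no | yes |
| 50+50 → 25+25 → 30+32 | 62/100 − 1 = −38% | 62/50 − 1 = +24% | 1.2 × 50 = 60; L = 32 | yes | no | yes |
| 100 → 50 → 62 | 62/100 − 1 = −38% | 62/50 − 1 = +24% | 1.2 × 50 = 60; L = 62 | yes | yes | yes |

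In the first row a tumour that has doubled would be recorded as stable. In the second, regrowth past 20% is missed. The third has one lesion and is both PR and PD under either reading, so the overlap is not caused by the mix of diameter and sum.

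**Step 3: overlap through a new lesion.** Let a single treated lesion go from 100 to 60 mm (−40%) at the first follow-up scan, with one new lesion. It meets PR, because PR does not exclude new lesions, and it meets PD through the new-lesion clause. No earlier scan is needed.

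**Step 4: when the overlap changes the reported rate.** With growth alone, PR and PD at one scan require 1.2 × Smin ≤ S ≤ 0.7 × S0, so Smin ≤ (0.7/1.2) × S0 = 0.58 × S0. The literal reading implies the same bound, since L ≤ S. An earlier scan had then already reached PR. A best-response rate is unchanged, while a rate read at a fixed visit can change. The new-lesion route has no such bound: at a first scan it decides whether the patient counts as a responder at all.

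**Step 5: weight of one patient.** Section 14.2 plans 90 patients, 60 with hepatocellular cancer, leaving 90 − 60 = 30 with cholangiocarcinoma. If all are in the denominator (an assumption), one changed call moves the response rate by 1/60 = 1.7 or 1/30 = 3.3 percentage points.

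**The case against.** The best defence is that the PD sentence has merely lost the words that would put the sum on both sides. Every reference in 10.2 is a sum, and the PR sentence also speaks of the primary lesion in the singular, so loose wording runs through the whole section. A sensible analyst would use the sum throughout. That is probably the intent, but the printed rule gives the wrong answer in step 2, and the repair in wording leaves the overlap in the third row and in step 3 untouched.

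A second defence is that naming RECIST brings in whatever that source says on several lesions and on precedence. The protocol gives no version, prints its own definitions and does not say that an outside text governs. What that text says cannot be checked from these documents.

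Some stronger readings are tempting and are not supported:

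- A reader might infer that PD is judged lesion by lesion, so that 80+20 mm becoming 40+24 mm is PR (sum −36%) and also PD (smaller lesion +20%). That needs the lesion's own earlier diameter as the reference, which 10.2 does not give. Under the literal reading and under the sum reading this scan is not PD.
- A reader might take all multi-lesion patients as misclassified. They are only exposed to the faulty sentence, and their number is not given.
- A reader might infer that the primary endpoint suffers, because 5.6 ends follow-up on the criteria in 5.5, which include progression. But 5.6 keeps such patients under observation for survival and 2-year local control, and local failure has its own definition in 10.3.

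**Conclusion.** The point holds as a minor correction to a secondary endpoint. The PD sentence is inconsistent with itself for patients with two or three lesions and, read literally, misses clear progression. Independently, PR and PD can both be true of one scan for any number of lesions, and the plan states no precedence and no rule for deriving the reported response.

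The number of patients affected cannot be derived, because the documents give neither the share with several lesions nor expected diameter changes or new-lesion rates. Discordance from growth is probably small. Even on the lesion-by-lesion reading that the text does not support, PR together with 20% growth of some lesion at the first scan occurs in about 0.0% to 0.5% of multi-lesion patients. That figure rests on assumptions: mean log change −0.3, standard deviation 0.30 to 0.45, between-lesion correlation 0.3 to 0.7, and baseline diameters uniform from 20 to 100 mm (two lesions) or 20 to 60 mm (three). It does not cover new lesions, for which no size can be given. The primary endpoint and the 94% and 7% figures stand.

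**What to change.** Amend 10.2 as follows:

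1. Define both categories on the sum of the longest diameters of all treated lesions. PR is a sum at least 30% below the baseline sum; PD is a sum at least 20% above the smallest sum, or any new lesion.
2. State that PD takes precedence when a scan meets both definitions.
3. State, in 10.2 or 14.4, whether the reported rate is best response or response at a fixed visit.

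Growth of a treated lesion beyond its pre-treatment extent remains captured as local failure under 10.3.

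The cost is a few lines of text. Tumour measurements are already scheduled in 9.1, so no visit, scan or patient is added. Any categories already assigned under the current wording should be rederived from the recorded diameters and new-lesion findings.
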